4.5. Trial Design

An open label, single arm, intervention study. This prospective multicentre study will recruit 70 individuals attending outpatient HIV services. Individuals will attend for visits at screening, baseline (first vaccine dose), week 4, week 8 (second vaccine dose), week 12, week 24 and week 48. Research and safety blood samples will be taken at each visit. Study participants will receive 2 intramuscular doses of HZ/su 2 months apart. For any individual who develops shingles after vaccination will have swabs taken for viral diagnosis and viral sequencing; these individuals will also have a blood sample taken. Tolerability of vaccination, including local and systemic adverse events will be recorded.

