4.6. Trial Assessment Schedule for Investigators (Table 1)

Visit number	1	2	3	4	5	6	7
	Screening*	Baseline					
Week number (window period)		0 (+ 8 weeks)	4 (+/-3 weeks)	8 (+/- 3 weeks weeks)	12 (+/-3 weeks)	24 (+/-3 weeks)	48 (+/-3 weeks)
Written informed consent	Х						
Eligibility assessment	Х	Х					
Demographics	Х						
Medical History	Х						
Vital Signs	Х	Х	Х	Х			
Temperature	Х	Х		Х			
Full Physical Exam	Х						
Directed Physical Exam		Х	Х	Х	Х	Х	Х
Concomitant medications	Х	Х	Х	Х	Х	Х	Х
Adverse events unsolicited AEs and SAEs and IMD review	х	х	х	х	х	х	х
Vaccination		Х		Х			
Solicited general Adverse Events (Table 3)			х		х		
Survey		Х					
Urine pregnancy test**	х	Х		х			
CD4 (CD4:CD8)		х					х
HIV viral load		Х				Х	Х
Hepatitis BsAg		Х					
Safety blood samples FBC, U&E, ALT		х				х	х
Blood samples for Immunology analysis		х	Х	Х	Х	Х	Х
Blood samples for Serology analysis		Х	Х	Х	Х	Х	х

*screening and baseline can occur on the same day

**Pregnancy test must be performed even if the subject is menstruating at the time of the study visit.

Table 2: Procedures to be performed for each suspected HZ case

Clinical history

Perform clinical examination

Collect samples from all sites with clinical suspicion of HZ (eg skin, CSF, vitreous fluid). The following samples should be taken from each site (there may be more than one site per person presentation.

- 1 swab to local lab for VZV PCR

- 1 swab to GOSH/University College London

Record relevant clinical information regarding HZ in eCRF by study staff/investigator including

- Date of onset of symptoms
- Location of symptoms
- Severity of symptoms
- Signs

Blood sample: ACD and SST tubes to be sent to Imperial College London laboratory (From Guys and St Thomas' NHS Foundation Trust or Imperial College NHS Healthcare Trust) or University of Oxford (from Oxford University Hospitals NHS Foundation Trust)

5. Trial Medication

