7.1. By Visit

This prospective multicentre study will recruit up to 70 individuals attending HIV services. Individuals will attend for visits at screening, baseline (vaccination), week 4, week 8 (vaccination), week 12, week 24 and week 48. Research and safety bloods will be taken at each visit. Study participants will receive 2 intramuscular doses of HZ/su 2 months apart. Vaccine reactogenicity review will occur 15 minutes post vaccination.

Any individual who develops shingles after vaccination will have swabs taken for viral diagnosis and viral sequencing.

The trial assessment schedule consists of a screening visit (visit 1) followed by an enrolment visit which defines week 0 (visit 2). If preferred by the participant, both visits can occur on the same day.

The first injection will take place at week 0 (visit 2) and the second injection visit is at week 8 (visit 4). Follow-up visits to ask about all adverse events and take blood are at weeks 12, 24 and 48 (visits 5,6,7). Additional visits may be undertaken if indicated, for example to investigate or follow-up an adverse event or abnormal laboratory result or if a participant develops symptoms suggestive of shingles.

The required volumes per visit together with sample collection and processing guidelines are described in detail in the laboratory manual. Required volumes of samples analysed by local laboratories (i.e. safety and HIV parameters) might vary according to local standard procedures. The visit windows are defined in the in Table 1.

Biological samples to be collected: -

Blood samples will be collected from all subjects at every visit to evaluate safety and/or immunogenicity. Should the participant experience a suspected HZ episode, swabs from the lesion and a blood sample will be collected.

Study details: Study subjects will be provided with a subject card which contains the address and telephone number of the main contact for information about the trial. The aim of this card is to inform any physician having to deal with a subject in an emergency situation that the subject is in a clinical trial and that he/she can contact the trial investigator for more relevant information. Subjects must be instructed to keep these cards in their possession at all times.

Study Assessments and Procedures

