- Directed physical exam
- Concomitant Medication review
- Vaccination
- Vaccine reactogenicity, unsolicited adverse event & IMD review
- Participant survey: beliefs about shingles and shingles vaccines
- Urine pregnancy test (women of childbearing potential only)
- Venepuncture for:
 - CD4 (CD4:CD8)
 - o HIV Viral Load
 - o Hepatitis BsAg
 - Safety blood sample (FBC, U&E, ALT)
 - Immunology blood sample
 - Serology blood sample

Note: Pregnancy test will be performed even if the subject is menstruating at the time of the study visit. The study vaccine can only be may only be administered if the pregnancy test is negative.

Check contraindications to vaccination: Contraindications to vaccination are to be checked at the beginning of each vaccination visit. Furthermore, any subject with a clinically diagnosed HZ episode between Visit 1 and Visit 2 should receive the second vaccination 3 months after the day of onset of shingles.

Vaccination Visits: 2 (Baseline) & 4

Prior to injection, study staff will conduct an inspection of the site where injections will be administered in each arm as part of the directed physical examination. The axillary, oral or tympanic body temperature of all subjects will be measured prior to any study vaccine administration. The preferred route for recording temperature in this study will be oral. All vaccines may be administered to persons with low-grade fevers, i.e., oral, tympanic on oral setting, or axillary temperature < 37.5°C. If a subject has an axillary/oral/tympanic on oral setting temperature \geq 37.5°C, it will constitute a contraindication to administration of vaccine.

Study staff should administer the injection into the deltoid muscle of the designated upper arm and record this in the appropriate CRF including the time of injection.

The Shingrix vaccine dose, after reconstitution, is 0.5 ml in volume and should be injected into the deltoid muscle of the non-dominant arm. Following injection participants should remain in clinic, in order to assess vaccine reactogenicity and solicited adverse events at 15 minutes following injection.

If the Investigator or delegate determines that the health on the day of vaccination temporarily precludes vaccination, the visit will be rescheduled within the window period for this visit.

The vaccinees will be observed for 15 minutes, with appropriate medical treatment readily available in case of anaphylaxis, following the administration of vaccine.

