All injections will be administered by delegated and suitably trained site staff.

Visit 3, week 4 (+/- 4 weeks)

The following will be conducted:

- Vital signs
- Directed Physical Exam
- Concomitant Medication Review
- Solicited and Unsolicited Adverse Event & IMD Review
- Venepuncture for:
 - Immunology blood sample
 - Serology blood sample

Visit 4, week 8 (-4/+7 weeks)

- Vital signs
- Temperature
- Directed Physical Exam
- Concomitant Medication Review
- Unsolicited Adverse Event & IMD Review
- Urine pregnancy test (women of childbearing potential only)

- Vaccination
- Venepuncture for:
 - Immunology blood sample
 - Serology blood sample

Visit 5, week 12 (+/- 4 weeks)

- Directed Physical Exam
- Concomitant Medication Review
- Solicited and Unsolicited Adverse Event & IMD Review
- Venepuncture for:
 - Immunology blood sample
 - Serology blood sample

Visit 6 week 24 (+/- 4 weeks)

- Directed Physical Exam
- Concomitant Medication Review
- Unsolicited Adverse Event & IMD Review
- Venepuncture for:
 - o HIV Viral load
 - o Safety blood sample
 - Immunology blood sample
 - Serology blood sample

Visit 7, week 48 (+/- 4 weeks)

- Directed Physical Exam
- Concomitant Medication Review
- Unsolicited Adverse Event & IMD Review
- Venepuncture for:
 - CD4 (CD4:CD8)
 - HIV Viral load
 - Safety blood sample
 - Immunology blood sample
 - Serology blood sample

Participant transfers

It is extremely unlikely that a participant will move from one trial centre to another, but not impossible. In the event that a participant does transfer, a copy of the participant's CRF should be provided to the new site and the participant will need to sign a new consent form. Once this has been done, the new site will take over responsibility for the participant; until this has been done, responsibility for the participant lies with the original site.

Recording of non-serious AEs and SAEs

• Refer to Section 8 for procedures for the Investigator to record AEs and SAEs.

• The subjects will be instructed to contact the investigator immediately should the subject manifest any signs or symptoms they perceive as serious.

Evaluation and confirmation of suspected and confirmed HZ cases

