9.2. Procedures for Recording and Reporting Adverse Events

The Medicines for Human Use (Clinical Trials) Regulations 2004 and Amended Regulations 2006 gives the following definitions:

- Adverse Event (AE): Any untoward medical occurrence in a participant to whom a medicinal product has been administered, including occurrences which are not necessarily caused by or related to that product.
- Adverse Reaction (AR): Any untoward and unintended response in a participant to an investigational medicinal product which is related to any dose administered to that participant.
- Unexpected Adverse Reaction (UAR): An adverse reaction the nature and severity of which is not consistent with the information about the medicinal

product in question set out in the summary of product characteristics (SmPC) for that product (for products with a marketing authorisation)

- Serious adverse Event (SAE), Serious Adverse Reaction (SAR) or Suspected Unexpected Serious Adverse Reaction (SUSAR): Any adverse event, adverse reaction or unexpected adverse reaction, respectively, that:
 - o results in death
 - o is life-threatening
 - o required hospitalisation or prolongation of existing hospitalisation
 - o results in persistent or significant disability or incapacity
 - o consists of a congenital anomaly or birth defect.
- Important Medical Events (IME) & Pregnancy: Events that may not be immediately life-threatening or result in death or hospitalisation but may jeopardise the participant or may require intervention to prevent one of the other outcomes listed in the definition above should also be considered serious. Although not a serious adverse event, any unplanned pregnancy will also be reported via the SAE reporting system.
 - Solicited adverse events: Subjects will be asked to report whether they had any solicited adverse experiences from Day 0 to Day 6 (7-day follow-up period) after each vaccine dose, to the clinical research team. All clinical signs and symptoms will be recorded by the investigator on the appropriate section of the eCRF. The following AEs (Table 3) will be solicited. General AEs are any experiences, which do not occur at the site of injection of a vaccine. They will be recorded as 'general' and include those events.

Table 3 Solicited adverse events

Pain at injection site
Redness at injection site
Swelling at injection site
Fatigue
Fever
† Gastrointestinal symptoms
Headache
Myalgia
Shivering

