10.3. Analysis

The analysis approach described below will be undertaken for both patient populations (PLWH aged \geq 50 and young adults with perinatally acquired infection). All continuous measures will be assessed for Normality, and we will apply a suitable transformation if appropriate (for example, by taking natural logarithms).

Primary endpoints:

1. Total VZV specific cell mediated titer change change from baseline to week 12 (4 weeks after second vaccine dose).

The individual values at baseline and week 12 will be presented on a dot plot. The values will be summarised as the geometric mean titer (GMT) ratio and its corresponding 95% confidence interval

2. Total VZV specific antibody titer change from baseline to week 12 (4 weeks after second vaccine dose)

The individual values at baseline and week 12 will be presented on a dot plot. The values will be summarised as the geometric mean titer (GMT) ratio and its corresponding 95% confidence interval

Secondary endpoints

3. Change of VZV specific cell mediated titer change from baseline to week 48

The individual values at baseline and week 48 will be presented on a dot plot. The values will be summarised as the geometric mean titer (GMT) ratio and its corresponding 95% confidence interval

4. Change of VZV specific antibody titer change from baseline to week 48

The individual values at baseline and week 48 will be presented on a dot plot. The values will be summarised as the geometric mean titer (GMT) ratio and its corresponding 95% confidence interval

5. Occurrence of adverse events (fatal and non-fatal, of all grades)

All AEs will be reported. The number and percentage with an adverse event and their severity will be presented in frequency tables. The number and percentage of participants reporting each solicited local and solicited systemic AE during the solicited 7-day follow-up period will be tabulated with exact 95% CIs after each vaccination visit and overall per participant

The duration of the solicited AEs, both local (for each vaccine separately) and systemic, during the 7-day follow-up period after each vaccination visit and overall

The number and percentage of participants reporting unsolicited AEs classified by MedDRA primary System Organ Class (SOC) and Preferred Term (PT) will be summarized along with exact 95% CIs following vaccination. This will be the same for SAEs & pIMDs.

6. Viral sequence of shingles infections

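### Beyond a 15-minute check, Day 0–6 solicited reactions are asked about only at Visits 3 and 5, nominally 22 days after Day 6, with no diary named; separately, the safety-blood statements contradict the schedule

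*Protocol*

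**What the plan says.** **Solicited reactions.** Section 9.2 asks each participant to tell the research team "whether they had any solicited adverse experiences from Day 0 to Day 6 (7-day follow-up period) after each vaccine dose". It then states that "All clinical signs and symptoms will be recorded by the investigator on the appropriate section of the eCRF". Its Table 3 lists injection-site reactions (pain, redness, swelling) and general ones (fatigue, fever, gastrointestinal symptoms, headache, myalgia, shivering).

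In Table 1 (section 4.6), the row "Solicited general Adverse Events (Table 3") is marked under Visits 3 and 5 only. The visit lists in section 7.1 agree: "Solicited and Unsolicited Adverse Event & IMD Review" appears at Visit 3 and Visit 5, while Visits 4, 6 and 7 list unsolicited events. At the two vaccination visits, participants stay in clinic so that staff can "assess vaccine reactogenicity and solicited adverse events at 15 minutes following injection".

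Section 10.3 plans, for each vaccination visit and overall, the number and percentage of participants with each solicited event and an exact 95% confidence interval. It also lists "The duration of the solicited AEs, both local (for each vaccine separately) and systemic, during the 7-day follow-up period".

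**Safety bloods.** Section 4.5 says "Research and safety blood samples will be taken at each visit", and the opening of section 7.1 says "Research and safety bloods will be taken at each visit". Table 1 and the individual visit lists place FBC, U&E and ALT at baseline, week 24 and week 48.

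**The concern.** The planned tables need day-level information: whether a reaction occurred in a given week, how severe it was, and when it began and ended. Section 5.3 describes short reactions, with a median of 2 to 3 days, and 1 to 2 days for severe ones. If the first question after the 15-minute check comes weeks later, with nothing written down at the time, counts and durations depend on memory. An exact confidence interval covers sampling error only; it does not reflect events forgotten or durations misremembered.

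Safety is secondary objective 6. Section 10.1 accepts that only common adverse events will be identified, so common, short-lived reactions are most of what the trial can say about safety in groups it describes as previously unresearched. An analysis plan cannot recover the detail if it was not recorded when the reaction occurred.

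The safety-blood issue is separate. Two statements in the text and two schedules give different instructions, and a site cannot follow both.

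**Working it through.** No stated figure needs to be reproduced. The check is visit-window arithmetic and a comparison of sections.

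**Inputs.** Solicited period: Day 0 to Day 6 (section 9.2). Windows from Table 1: Visit 3 at 4 ± 3 weeks, Visit 4 (dose 2) at 8 ± 3, Visit 5 at 12 ± 3. Windows from section 7.1: Visit 3 at 4 ± 4 weeks, Visit 4 at 8 −4/+7, Visit 5 at 12 ± 4. Section 7.1 refers to Table 1 for the windows and then lists different ones.

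**Formula.** Lag = (days from dose to the visit at which solicited events are asked about) − 6.

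**Nominal.** Dose 1 to Visit 3: 4 × 7 = 28 days; lag 28 − 6 = 22 days. Dose 2 to Visit 5: (12 − 8) × 7 = 28 days; lag 22 days.

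**Dose 1 to Visit 3, limits.**
- Table 1: earliest (4 − 3) × 7 = day 7, lag 1 day; latest (4 + 3) × 7 = day 49, lag 43 days.
- Section 7.1: earliest (4 − 4) × 7 = day 0, before the seven days have passed; latest (4 + 4) × 7 = day 56, lag 50 days.

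**Dose 2 to Visit 5, limits.** The protocol does not say where the Visit 5 window is anchored.
- Counted from the actual second dose, which fits the description of week 12 in section 4.2 as four weeks after that dose: latest 4 + 3 = 7 weeks (Table 1) or 4 + 4 = 8 weeks (section 7.1).
- Counted from week 0: latest 15 − 5 = 10 weeks (70 days, lag 64) under Table 1, or 16 − 4 = 12 weeks (84 days, lag 78) under section 7.1. At the other end, 9 − 11 = −2 weeks or 8 − 15 = −7 weeks, so the windows alone would not guarantee that Visit 5 follows dose 2.

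**What is named between the dose and the visit.** The 15-minute check covers only the first minutes of Day 0. Section 9.2 describes reporting to the team and entry by the investigator. No diary, telephone call or Day 7 contact is named. Fever is on the solicited list, but Table 1 marks temperature only at screening, baseline and Visit 4.

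**Safety bloods, side by side.**

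| Source | Visits with safety bloods |
|---|---|
| Sections 4.5 and 7.1 (opening) | every visit |
| Table 1 | baseline, week 24, week 48 |
| Section 7.1 visit lists | baseline, week 24, week 48 |

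The schedules therefore include 3 of 7 visits, with none at screening or at weeks 4, 8 and 12. Under them, the first safety sample after dose 2 is nominally 24 − 8 = 16 weeks later.

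**The case against.** Several objections have force.

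- **Other capture routes exist.** A reader might infer that safety in the vaccination phase goes unrecorded as it happens. The protocol does not support that. Unsolicited events, SAEs and immune-mediated disease are reviewed at every visit. Participants must contact the investigator at once about symptoms they perceive as serious, and they carry a trial contact card. SAEs and potential immune-mediated diseases are reported within 24 hours. The point is confined to solicited reactions.
- **No diary is named, but none is excluded.** Section 9.2 does not restrict reporting to visits, and a diary could sit in a working document not shown. This stands as a caveat. If one exists, the protocol should name it as the source, because section 9.2 describes only reporting to the team and investigator entry.
- **The longest recall intervals depend on the anchor.** The 10- and 12-week figures arise only if both windows run from week 0. Section 4.2 supports 7 or 8 weeks. Visit 3 can also fall early. The nominal 22 days does not depend on the anchor, and section 3 explains the wide windows by the younger participants' difficulty with regular attendance, so late visits are foreseeable.
- **The vaccine is licensed and its safety has been studied elsewhere.** This limits the weight of the point but does not make the planned tables better founded.
- **Safety bloods.** A reader might infer that laboratory events after vaccination will be missed. That is speculative: no laboratory endpoint is defined, extra visits for abnormal results are allowed, and a sample at week 4, 8 or 12 could also miss a short-lived change. Section 7 refers to Table 1 for procedures, and section 7.1 says elsewhere that blood is collected for safety and/or immunogenicity. What remains is a contradiction in the text, not a demonstrated gap in the design.

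**Conclusion.** The concern holds for solicited reactions. As written, Day 0–6 reactions are asked about nominally 22 days after Day 6, and up to 7 weeks (Table 1) or 8 weeks (section 7.1) after the dose, or longer for dose 2 if the Visit 5 window runs from week 0. Per-dose frequencies and durations would then rest on recall and may be under-reported. Neither the size of that under-reporting nor the error in durations can be computed from the protocol.

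This assumes that no diary is specified elsewhere, and that the durations in section 5.3 apply here; that section gives them for adults aged 50 and over and calls the profile in immunocompromised adults consistent. The primary immunogenicity endpoints are not affected. The point should be corrected for the secondary safety analysis.

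The safety-blood contradiction between sections 4.5 and 7.1 (opening) and Table 1 with the visit lists is real, and it is a matter of wording to be settled.

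**What to change.** Give each participant a seven-day diary card, paper or electronic, at each dose. For each Table 3 reaction it should record start date, stop date and grade. Staff review it at the next visit and enter it in the eCRF. Name it in section 9.2 and state in section 10.3 that it is the source for the solicited-event tables. The cost is a form and its transcription; no visit is added. If a diary already exists in a working document, a sentence naming it is enough.

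State whether the Visit 5 window is counted from week 0 or from the actual second dose, and reconcile the windows in Table 1 with those in section 7.1.

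Reconcile the safety-blood statements in sections 4.5 and 7.1 with Table 1 and the visit lists. Which schedule applies is for the sponsor to decide. Correcting the text costs only wording. If the every-visit statement is kept, the cost is local laboratory tests: blood is already drawn at weeks 4, 8 and 12 for immunology and serology, whereas screening has no scheduled blood draw and would need one.

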9.3. Protocol vaccine discontinuation

In consenting to the trial, participants are consenting to receive vaccines, to attend the visits for trial follow-up and to provide information that supports data collection.

An individual participant may stop injections early or be stopped early for any of the following reasons:

- Pregnancy in the participant
- > Unacceptable toxicity that precludes further injections
- Intercurrent illness that prevents further injections including emergent conditions that meet the exclusion criteria
- > Withdrawal of consent for injections by the participant

A decision to discontinue further injections should be taken in consultation with the local PI.

